7. STUDY TREATMENT DISCONTINUATION AND SUBJECT DISCONTINUATION / WITHDRAWAL FROM THE STUDY

7.1. Discontinuation of Study Treatment for an Individual Subject

Study treatment discontinuation, interruption or dose reduction will be considered if subjects experience the following:

- TEAE of Grade 3 or 4 (per CTCAE V5.0) with severity and relationship noted below
- Any suspected statin-related AE, as determined by the investigator (see below)
- Laboratory result(s) indicative of drug induced liver disease (DILI), based on assessment by the Medical Monitor and by the independent DILI adjudication
- Confirmed diagnosis of HCC
- Progression from Child-Pugh A to Child-Pugh B or C status
- Liver decompensation events
- Subjects with MELD score ≥ 15 .

7.1.1. Specific Actions Taken Will Be As Follows:

- i) TEAE of Grade 3 or 4 (per CTCAE V5.0):
 - Any possibly or probably related Grade 3 TEAE, aldafermin and/or statin may be discontinued or interrupted; evaluation and determination by the PI or the unblinded Medical Monitor in the case of TEAEs possibly related to statin use.
 - Any Grade 4 or higher TEAE, aldafermin and statin will be discontinued
- ii) Any suspected statin-related AE:

Subjects will be allowed a rosuvastatin dose adjustment if the subject experiences a statin-related AE (as determined by the PI). The third-party Medical Monitor will be contacted by the study site to report a possible statin-related AE requiring intervention. Information will be collected on the AE including the specific description, history, and severity based on CTCAE grading. The study team should instruct the subject to refrain from administering the rosuvastatin/placebo therapy and to repeat safety laboratory examinations as indicated by the specific AE within 72 hours. If the subject is <2 weeks from their next visit, they should not dose the rosuvastatin/placebo therapy until the next scheduled visit. If they are >2 weeks from their next study visit, an unscheduled visit should be made to repeat laboratory examinations.

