If the AE resolves, subjects will be restarted on a lower dose of over encapsulated rosuvastatin. Subjects on rosuvastatin 20 mg or 40 mg will be restarted on rosuvastatin 10 mg, and subjects on 5 mg or 10 mg will be restarted on rosuvastatin 5 mg. Subjects taking over-encapsulated placebo will be restarted on placebo. In the event that the AE re-occurs upon re-initiation at the lower dose, over encapsulated rosuvastatin/placebo should be discontinued. If the AE does not re-occur with the lower dose, an increase in the over encapsulated rosuvastatin dose may be considered at the subsequent clinic visits according to the protocol algorithm. If the AE re-occurs following administration of this new dose of

rosuvastatin, over encapsulated rosuvastatin/placebo may be reverted to the last tolerated dose. Aldafermin dosing will not be interrupted.

If a subject experiences a statin-related AE of myalgia or rhabdomyolysis (as determined by the PI), information will be collected on the AE including the specific description, history, and severity based on CTCAE grading and forwarded to the designated third-party Medical Monitor who is blinded to treatment assignment but unblinded to laboratory data and statin assignment and dose. The clinical study team will collect a blood sample for safety laboratory evaluations within 48-72 hours. For subjects that have signs or symptoms suggestive of rhabdomyolysis from either muscle symptoms (such as myalgia, pain, weakness, dark urine) or elevated creatine kinase (CK), the origin of the symptoms/CK elevation will be investigated. To this end, the subject will be interviewed about recent heavy exercise, trauma, convulsions, surgery, use of excessive alcohol, morphine, cocaine, or other contributing factors. Additional laboratory tests (creatinine, AST/ALT, total and conjugated bilirubin, potassium, calcium, and/or myoglobin (serum and urine)) will also be performed.

If the subject experienced statin-related increased CK>3 x ULN with clinical symptoms, administration of over-encapsulated rosuvastatin/placebo should be held and may be re-initiated at half the prior dose if follow-up CK is <3 x ULN. If CK rises to >3 x ULN again, the administration of over-encapsulated rosuvastatin/placebo should be held until CK <3 x ULN and can be re-initiated at 5 mg. For subjects experiencing symptoms and CK elevation on 5 mg, over-encapsulated rosuvastatin/placebo should be discontinued.

Aldafermin dosing will continue.

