For subjects with suspicion of statin-related myalgia or rhabdomyolysis AND CK 3-5 x ULN, administration of over-encapsulated rosuvastatin/placebo should be held until CK<3 x ULN and may be reinitiated at half the original dose. If symptoms persist and if CK increases >3 x ULN, rosuvastatin should be discontinued. For CK>5 x ULN with clinical suspicion of rhabdomyolysis (ruling out other causes, e.g., recent heavy exercise, trauma, convulsions, surgery, use of excessive alcohol, morphine, cocaine, or other contributing factors), rosuvastatin will be discontinued. Throughout, aldafermin dosing should continue.

iii) Laboratory value(s) suggestive of DILI:

- a) Elevation of AST or ALT >2 x above subject-specific baseline value (calculated using the average of the Day -56 and the Day 1 values) and total bilirubin >1.5 x subject specific baseline value, repeat testing of ALT, AST, and bilirubin must be performed within 48-72 hours. If there are persistent elevations (AST or ALT >2 x baseline or TBL >1.5 x baseline values) upon repeat testing, then close observation (testing and physical examination 2-3 times per week) should be implemented and discontinuation of aldafermin and rosuvastatin should be considered (see below). Note: the unblinded study Medical Monitor will be notified of acute suspected cases and upon identification of suspected DILI cases, the Liver Events Adjudication Committee chair will be notified.
- b) A decision to discontinue or temporarily interrupt the study drug will be considered based on factors that include how much higher than baseline ALT and AST were relative to the ULN and how much the on-study ALT and AST levels have increased

relative to baseline, in addition to whether there is concomitant elevation of bilirubin or INR. aldafermin and rosuvastatin will be discontinued or temporarily interrupted as follows:

- If baseline measurements (BLM) were $<2 \times$ ULN, discontinue if ALT or AST increases to $>5 \times$ BLM
- If BLM $\geq 2 \times$ ULN but $<5 \times$ ULN, discontinue if ALT or AST increases to $>3 \times$ BLM
- Discontinue if ALT or AST increase $>2 \times$ BLM AND the increase is accompanied by a concomitant increase in TBL to $>2 \times$ BLM OR the INR concomitantly increases by >0.2
- Discontinue if total bilirubin $>3.0 \text{ mg/dL}$
- In any subjects with signs and symptoms of fatigue, nausea, vomiting, right upper quadrant pain or tenderness, fever, rash, and/or eosinophilia ($>5\%$).

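### Section 7.1.1 gives opposite aldafermin instructions for a Grade 4 statin-related event, and its muscle-event rules give two answers at rosuvastatin 5 mg

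*Protocol*

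**What the plan says.** Section 7.1.1 lists the actions that follow particular events.

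**Part i** works by CTCAE grade. Its Grade 3 bullet leaves stopping or interrupting to judgement and names the unblinded Medical Monitor as decision-maker "in the case of TEAEs possibly related to statin use", so part i plainly reaches statin-related events. Its next bullet reads "Any Grade 4 or higher TEAE, aldafermin and statin will be discontinued".

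**Part ii** works by suspected cause and covers any event thought to be statin-related.
- General rule: "If the AE resolves, subjects will be restarted on a lower dose of over encapsulated rosuvastatin". From either of the two higher strengths, 20 and 40 mg, the restart dose is 10 mg. For the two lower strengths the rule is that "subjects on 5 mg or 10 mg will be restarted on rosuvastatin 5 mg". Recurrence at the lower dose leads to discontinuation of the capsule. The rule closes with "Aldafermin dosing will not be interrupted".
- First muscle rule (symptoms with CK above 3 times ULN): hold, then possibly half the prior dose; for symptoms with CK elevation on 5 mg, discontinue. Aldafermin continues.
- Second muscle rule (suspected myalgia or rhabdomyolysis with CK 3 to 5 times ULN): hold, then possibly half the original dose. Above 5 times ULN with suspected rhabdomyolysis, rosuvastatin stops. This text ends "Throughout, aldafermin dosing should continue".

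Section 6.1.3 lists the supplied strengths as 5, 10, 20 and 40 mg.

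**The concern.** A Grade 4 event that the investigator attributes to the statin falls under both parts. Part i takes the subject off aldafermin; part ii keeps the subject on it. A site cannot follow one without breaching the other, and the choice decides whether a subject with a severe event remains on the investigational drug.

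For muscle events, overlapping rules mean that two subjects with the same event and the same dose could be handled differently, each within the protocol. These are operative safety instructions, so the place to settle them is the protocol itself.

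**Working it through.** No sample size, power or event figure is involved. The check compares the trigger and outcome of each rule and asks whether one subject can meet two rules with different outcomes.

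**Step 1. Can a Grade 4 event fall under both parts?** Part i excludes no cause: its Grade 4 bullet applies to any such event, and the bullet above it names statin-related ones. Part ii excludes no grade. It has grade recorded, for muscle events as "severity based on CTCAE grading and forwarded to the designated third-party Medical Monitor", but never uses grade to limit the rule. The two scopes therefore overlap, and no outside CTCAE cut-off for CK is needed to show it.

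**Step 2. Aldafermin at Grade 4.** Part i: discontinue. Part ii: not interrupted (general rule), continues (both muscle rules). These conflict in every case.

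**Step 3. Statin at Grade 4.** Part i discontinues it in every case. Part ii depends on the situation:

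| Situation under part ii | Part ii statin action | Against part i |
|---|---|---|
| General event that resolves | restart | conflict |
| Symptomatic CK rise where a half-dose restart is permitted | may restart | conflict |
| CK above 5 times ULN with suspected rhabdomyolysis, second muscle rule | discontinue | agree |
| Symptomatic CK elevation on 5 mg, first muscle rule | discontinue | agree |
| Recurrence at the lower dose, general rule | discontinue | agree |

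**Step 4. Restart dose after a first symptomatic event with CK 3 to 5 times ULN.** Such a subject meets the first muscle rule (CK above 3 times ULN) as well as the second. The halving rules give dose / 2.

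| Dose at event | General rule | First muscle rule | Second muscle rule |
|---|---|---|---|
| 40 mg | 10 mg | 40 / 2 = 20 mg | 40 / 2 = 20 mg |
| 20 mg | 10 mg | 20 / 2 = 10 mg | 20 / 2 = 10 mg |
| 10 mg | 5 mg | 10 / 2 = 5 mg | 10 / 2 = 5 mg |
| 5 mg | 5 mg | discontinue | 5 / 2 = 2.5 mg |

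The rules agree at 10 and 20 mg and differ at 40 and 5 mg. If the muscle rules are meant to replace the general rule, the 40 mg difference disappears and the 5 mg difference remains: discontinue against 2.5 mg, which Section 6.1.3 does not supply. Separately, the general rule describes its restart as a reduction, yet sends 5 mg back to 5 mg.

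**Step 5. Two smaller points.** Part iii c sends locally run tests in suspected drug-induced liver injury to the investigator site, while Table 8 footnote j withholds ALT and AST from site and sponsor from Week 2; no sentence links the two. Section 8.4.2 refers management of statin-related events to Section 8.3.17, which covers LDL-C goals and titration and holds no such rule; the Synopsis and Section 4.1 point to Section 7.1.1 part ii.

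**The case against.** The best defence is that the two parts can be read together. Part i sets a stop by grade for all events. Part ii opens as an allowance for rosuvastatin dose adjustment, so its aldafermin sentences may mean only that holding the statin does not by itself interrupt aldafermin. That reading is possible, but so is the reverse, in which the rule specific to statin events governs. The two point in opposite directions and the protocol endorses neither. The objection shows that the repair is short, not that it is unnecessary.

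The defence is right to limit the wider readings that the text may invite.
- A reader might infer that both drugs conflict for every statin-related event at every dose. Step 3 shows otherwise for the statin, and the general restart applies only once the event has resolved.
- A reader might infer that the muscle rules contradict each other throughout. On a repeat CK rise, the first rule speaks of CK alone while the second adds persisting symptoms, so they can be read as successive cases. The rule above 5 times ULN can be read as a narrower, more serious exception. The muscle paragraphs as a whole read naturally as a special case of the general rule, though this is not stated.
- A reader might infer that local liver testing breaches the blind. The blinding text is attached to scheduled chemistry, and part iii a brings in the unblinded monitor. What is missing is a reconciling sentence.

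It is also fair that one third-party Medical Monitor handles statin dosing, which limits inconsistent practice, and that the halving is permissive. That 2.5 mg cannot be dispensed confirms a defect at 5 mg; it does not tell the reader which instruction was intended.

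**Conclusion.** The point holds with this scope. For aldafermin, parts i and ii conflict for every Grade 4 statin-related event. For the statin, they conflict only where part ii allows a restart. At rosuvastatin 5 mg, a first symptomatic event with CK 3 to 5 times ULN has two different outcomes under the muscle rules, whichever way the general rule is read. At 40 mg there is a difference only if the general rule also applies to muscle events.

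The conclusion rests on the absence of any stated precedence or grade limit in Section 7.1.1. The number of affected subjects cannot be estimated from the protocol, and no effect on the ELF analysis is claimed. It should be fixed because it governs continued dosing after a severe event. The local liver-test route and the Section 8.3.17 reference are minor.

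**What to change.** The sponsor's clinical team should reconcile parts i and ii of Section 7.1.1. The amended text should state which part takes precedence for a Grade 4 statin-related event, for each drug. It should also state how the general restart rule and the two muscle rules relate to one another, so that each event and dose, 5 mg and 40 mg in particular, leads to one action that the supplied strengths allow. Which clinical rule applies is for that team to decide.

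In the same amendment, align part iii c with Table 8 footnote j on who may see local ALT and AST results, and correct the Section 8.3.17 reference in Section 8.4.2.

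The cost is amendment wording and one corrected cross-reference, with no new visits, samples or subjects.

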LDL-C values will be further evaluated at study visit Week 6, 12, 18, 24, 30, 36, and 42, in order to identify subjects who require rosuvastatin initiation or dose-escalation. Specific LDL goal or treatment success criteria are described in detail in [Section 8.3.17](#). Subjects who do not meet rosuvastatin increase criteria will continue on their prior assigned dose of over-encapsulated rosuvastatin/ matched placebo. Subjects on the maximum dose of rosuvastatin 40 mg whose LDL-C levels are still not at goal will continue on the study with rosuvastatin 40 mg unless the subject experiences a cardiovascular-related SAE (e.g., myocardial infarction, CVA). Subjects experiencing a CV-related SAE on rosuvastatin 40 mg will discontinue both aldafermin and rosuvastatin for the remainder of the trial, and cardiovascular care will continue per the subject's regular physician and as per local standard of care practices. Subjects who experience rosuvastatin-related intolerance (by evaluation of muscular symptoms and creatine kinase (CK) levels) will be evaluated by follow-up laboratory testing after the over-encapsulated rosuvastatin/placebo has been held. Depending on the CK levels and clinical status, subjects may be allowed to restart over-encapsulated rosuvastatin/placebo at a reduced dose. Algorithm details are found in [Section 7.1.1](#), part ii.

All subjects will be assessed at Weeks 49 and 54 to confirm their LDL-C levels have decreased to near baseline, at which point no additional follow-up is needed.

Subjects who do not meet LDL-C decrease criteria at Week 54 will have an additional 4-week follow-up visit at Week 58 to confirm that their LDL-C level returned to near baseline. Subjects may remain on statin through Week 58.

As part of safety monitoring, subjects will undergo ultrasound and alpha fetoprotein (AFP) testing at Weeks 24 and 48 to screen for HCC. Subjects with new lesions ≥ 10 mm with AFP > 20 ng/mL will be treated according to local guidelines. If new lesions ≥ 10 mm with AFP > 20 ng/mL occur at Week 24, subjects may continue on study drug at the discretion of the investigator unless or until a clinical diagnosis of HCC is made (defined as LI-RADS 4 or 5 on MRI, or histological confirmation of HCC). For subjects with suspected HCC by ultrasound and AFP screening, additional imaging may be obtained, and data will be gathered for adjudication.

Overall safety will be monitored by a data safety monitoring board (DSMB).

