6.1.3. Rosuvastatin / Placebo

Commercial rosuvastatin tablets will be over-encapsulated and will be supplied as 5 mg, 10 mg, 20 mg, or 40 mg strengths in multi-count bottles. Inactive ingredient microcrystalline cellulose will be used to backfill over-encapsulated rosuvastatin calcium tablets.

Placebo capsules for rosuvastatin calcium contains only microcrystalline cellulose and will be supplied in multi-count bottles. The capsules used for the active and placebo are opaque, Swedish Orange, size A, hard gelatin capsules containing gelatin, titanium oxide, and FDA/E172 red iron oxide. Refer to [Appendix 5](#) for the rosuvastatin package inserts.

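### Protocol 7.1.1 ii) has overlapping statin-intolerance rules with no precedence; for muscle symptoms with CK 3-5 x ULN on rosuvastatin 5 mg they give stop, 2.5 mg and 5 mg

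*Protocol*

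**What the plan says.** The Synopsis and Section 4.1 both name Section 7.1.1, part ii, as the place where the statin-intolerance algorithm is set out. Section 4.1 summarises it by saying that, depending on CK and clinical status, "subjects may be allowed to restart over-encapsulated rosuvastatin/placebo at a reduced dose". Part ii then contains three sets of instructions.

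- **General rule for any suspected statin-related adverse event.** Once the event resolves, the subject restarts at a lower dose. Subjects on 20 or 40 mg go to 10 mg, while "subjects on 5 mg or 10 mg will be restarted on rosuvastatin 5 mg". On recurrence: "In the event that the AE re-occurs upon re-initiation at the lower dose, over encapsulated rosuvastatin/placebo should be discontinued". If there is no recurrence the dose may later be raised again, and if the event then returns the subject may go back to the last dose tolerated.
- **First CK paragraph, for CK above 3 x ULN with symptoms.** Hold, then half the prior dose is allowed once CK is below 3 x ULN. If CK goes above 3 x ULN again, treatment "should be held until CK <3 x ULN and can be re-initiated at 5 mg". The paragraph ends: "For subjects experiencing symptoms and CK elevation on 5 mg, over-encapsulated rosuvastatin/placebo should be discontinued".
- **Second CK paragraph, for suspected myalgia or rhabdomyolysis with CK 3-5 x ULN.** Treatment "should be held until CK<3 x ULN and may be reinitiated at half the original dose". Then: "If symptoms persist and if CK increases >3 x ULN, rosuvastatin should be discontinued". For CK above 5 x ULN with clinical suspicion of rhabdomyolysis and other causes ruled out, rosuvastatin is stopped.

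Section 6.1.3 says that rosuvastatin "will be supplied as 5 mg, 10 mg, 20 mg, or 40 mg strengths in multi-count bottles", and Section 6.2.1.2 has subjects take one capsule a day. Section 8.4.2 sends subjects who need a statin dose reduction or stop to Section 8.3.17 for management.

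**The concern.** A subject with statin-related myalgia and CK of, say, 4 x ULN falls under all three sets at once. Part ii does not say which prevails. Where the sets differ, the choice between re-exposing a cirrhotic subject with muscle symptoms and raised CK, and stopping the statin, depends on which paragraph is applied.

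The 5 mg level is not a rare corner. Under Sections 4.1 and 8.3.17 it is the starting dose for every statin-naïve subject who begins active rosuvastatin. The site cannot resolve the matter at the bedside either, because sites and sponsor are blinded to the rosuvastatin dose. The third-party Medical Monitor has to apply the written rule.

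The cross-reference in Section 8.4.2 does not help: Section 8.3.17 deals with LDL-C goals and titration and has no rule for a statin-related adverse event.

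**Working it through.** No power or error-rate arithmetic applies. The check is to apply each rule set to each supplied strength for a subject with muscle symptoms and CK 4 x ULN, which satisfies every trigger.

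**Inputs.** Strengths 5, 10, 20 and 40 mg (Section 6.1.3); one capsule a day (Section 6.2.1.2); the three rule sets (Section 7.1.1 ii).

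**Step 1: first event.** Half doses are 40/2 = 20, 20/2 = 10, 10/2 = 5 and 5/2 = 2.5 mg.

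| Dose at event | General rule | First CK paragraph | Second CK paragraph |
|---|---|---|---|
| 40 mg | 10 mg | 20 mg | 20 mg |
| 20 mg | 10 mg | 10 mg | 10 mg |
| 10 mg | 5 mg | 5 mg | 5 mg |
| 5 mg | 5 mg | stop | 2.5 mg |

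The rules agree at 10 and 20 mg and differ at 40 and 5 mg, so at 2 of the 4 strengths.

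- *At 5 mg* there are three different instructions. The 2.5 mg restart cannot be dispensed: no such strength exists and the regimen is one capsule daily. The 5 mg restart also fails the general rule's own promise of a lower dose and Section 4.1's reduced dose. The stop (should) and the general rule's restart (will) are both directive.
- *At 40 mg* the restart dose differs by a factor of 20/10 = 2.

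**Step 2: CK above 3 x ULN again, with symptoms, after the restart.**

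| Starting dose | General rule | First CK paragraph | Second CK paragraph |
|---|---|---|---|
| 40 mg | stop (recurrence at 10 mg) | hold; 5 mg allowed (from 20 mg) | stop if symptoms persist (from 20 mg) |
| 20 mg | stop (recurrence at 10 mg) | hold; 5 mg allowed (from 10 mg) | stop if symptoms persist (from 10 mg) |
| 10 mg | stop (recurrence at 5 mg) | stop (its own 5 mg sentence) | stop if symptoms persist (from 5 mg) |

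From 10 mg all three lead to a stop. From 40 and 20 mg the first CK paragraph permits a 5 mg restart and attaches no symptom condition to it. The second CK paragraph requires a stop when symptoms and CK go together.

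**Step 3: CK above 5 x ULN.** The half-dose restart in the first CK paragraph has no upper CK limit. The second CK paragraph stops rosuvastatin when rhabdomyolysis is suspected. Which prevails is not stated, although the second reads naturally as the specific case, and Section 7.1.1 i) stops the statin for any Grade 4 event.

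**The case against.** The best defence is that a specific rule overrides a general one. The muscle paragraphs follow the general rule and carry their own tests, thresholds and doses. On that reading the general rule's 5 mg restart drops out and so does the 40 mg discrepancy. At 5 mg what remains is a stop written expressly for that dose, against an optional half dose that cannot be supplied. The only action that can be carried out is to stop. This is a sensible reading and probably the one intended, but the text does not state it. It also does not settle the two CK paragraphs against each other, since both are specific to muscle events and both cover CK 3-5 x ULN.

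For the second CK rise the defence is stronger. The 5 mg restart turns on CK alone and is permissive. The stop in the second CK paragraph needs symptoms as well and is worded as what should happen. Read together, a rise without symptoms may go to 5 mg and a symptomatic one stops. The second CK paragraph also speaks of symptoms persisting rather than returning. This objection stands: the point is an ambiguity that wants a clarifying phrase, not a contradiction.

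A reader might go further and count rechallenges, inferring that the first CK paragraph permits two where the other rules permit one. The text does not support that count. Under the general rule a subject who tolerates the lower dose may be titrated up again and, if the event returns, go back to the last tolerated dose, which is continued exposure after a recurrence. That rule's recurrence stop also attaches to its own 10 mg restart from 40 mg, so a subject on 20 mg after a half-dose restart is not on its path.

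The practical reach is limited. A Medical Monitor who knows the dose and the laboratory values handles each muscle case, Grade 3 and 4 events have their own provisions, and subjects with known statin intolerance are excluded.

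**Conclusion.** The point holds as a drafting conflict in a safety algorithm. It is clear in one state: muscle symptoms with CK 3-5 x ULN on 5 mg, where the three rules give stop, an unavailable 2.5 mg, and 5 mg. It also holds for the restart dose after a first event on 40 mg (10 versus 20 mg), unless one assumes that the muscle paragraphs displace the general rule. Symptomatic CK recurrence after a half-dose restart from 40 or 20 mg is a weaker ambiguity that can be reconciled. The unstated precedence above 5 x ULN is softer still. The Section 8.4.2 reference is a clerical error.

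The protocol gives no rate for these events, so the number of subjects affected cannot be estimated. The Appendix 4 chart was not legible in the copy reviewed and was not used. The Synopsis and Section 4.1 point to Section 7.1.1 ii), not to that chart, for intolerance. The effect is on statin safety management only. Nothing here bears on the ELF analysis.

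**What to change.** In Section 7.1.1 ii):

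1. State that for muscle or CK events the two CK paragraphs override the general rule's restart doses and its action on recurrence. Subjects on matched placebo still restart on placebo.
2. Add to the second CK paragraph that symptoms with CK above 3 x ULN on 5 mg mean discontinuation.
3. Limit the 5 mg re-initiation in the first CK paragraph to a second CK rise without symptoms. A symptomatic recurrence means discontinuation.
4. State that CK above 5 x ULN with suspected rhabdomyolysis, other causes ruled out, means discontinuation with no restart.

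In Section 8.4.2, change the reference from Section 8.3.17 to Section 7.1.1 ii).

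Every dose and stop used here is already in the protocol. The cost is a few sentences, one corrected reference, and a check that the third-party Medical Monitor's instructions match. No new strength, visit or test is needed. The edit leaves one thing as it is: the half-dose restart for symptomatic CK above 5 x ULN when rhabdomyolysis is not suspected. Whether that is wanted is a clinical decision for the sponsor.
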